6.3.4. Bates-Jensen Wound Assessment Tool

The PI or research staff will administer the Bates-Jensen Wound Assessment Tool (BWAT) at the Initial Visit in order to gain an understanding of the wound characteristics. The instructions for use for the BWAT are provided in Section 11.3.3.1, with the actual tool that will serve as the CRF in Section 11.3.3.2. In order to convert the BWAT into a tool that is compatible with the idiosyncrasies of this study, a few minor changes were made. The field for “Name” was changed to “Subject Number.” In addition, a field for “Date” and “Wound Assessment Number” were listed for tracking purposes, given the multiple visits that will occur with this study. Also, the BWAT contains three columns for scoring, each corresponding to a separate date and assessment. In this study there will likely be more than three visits for each subject, so we have deleted two of the columns to avoid confusion; a new BWAT CRF will be used for each visit. Similarly, the instructions to plot multiple scores on visual scale provided at the bottom of the assessment was removed; the score from that visit will be plotted elsewhere, and the trajectory of the scores will be analyzed after study completion using data from all visits.

6.3.5. Dressing Application

Following the wound assessment, the Investigator or other clinician on the research staff will cleanse the wound using a wound cleansing solution and apply the Puracol® Ultra Powder

dressing to the wound. A notation as to the type of secondary dressing applied will be noted on the Dressing Log CRF (see Appendix 11.3.4).

6.4. Dressing Change Visit

Participants will visit the clinic for a dressing change twice weekly. Ultimate determination of dressing change frequency will reside with the PI, in the event the twice weekly visits conflicts with the patient's clinical needs. During these visits, participants will be assessed for any Adverse Events (AEs) and have their dressing changed. Documentation of the dressing change will be captured in the Dressing Log CRF, available in Appendix 11.3.4.

6.5. Wound Assessment Visit

One of the dressing change visits will serve as the wound assessment visit as well. Participants will come to the clinic every 7 days \pm 2 days so the PI can assess the wound. The assessments conducted at this visit will be identical to those described in Sections 6.3.2 to 6.3.4. Additionally, if the participant is due for a dressing change, one will occur at this visit as well. All events will be documented via the Wound Photograph, BWAT, and Dressing Log CRFs.

6.6. Final Visit

The Final Visit will take place 12 weeks after participant enrollment; in the event the wound completely heals before 12 weeks have passed, the visit where the PI notes complete wound healing will serve as the Final Visit. Data collection will follow the same procedures defined in Sections 6.3.1 to 6.3.4.

7. ADVERSE EVENTS

7.1. Definition of Adverse Event

The FDA definition for an AE will be used in this study: Adverse event means any untoward medical occurrence associated with the use of an intervention in humans, whether or not considered intervention related.

7.2. Definition of Serious Adverse Event

The FDA definition of a Serious Adverse Event (SAE) will be used in this study: An AE or suspected adverse reaction is considered "serious" if, in the view of either the PI or Sponsor, it results in any of the following outcomes:

- Death
- A life-threatening adverse event
- Inpatient hospitalization or prolongation of existing hospitalization
- A persistent or significant incapacity or substantial disruption of the ability to conduct normal life functions or,
- A congenital anomaly/birth defect.

Important medical events that may not result in death, be life-threatening, or require hospitalization may be considered serious when, based upon appropriate medical judgment, they may jeopardize the participant and may require medical or surgical intervention to prevent one of the outcomes listed in this definition.

7.3. Severity of Adverse Event

- **Mild:** Awareness of signs or symptoms, but easily tolerated; are of minor irritant type, causing no loss of time from normal activities; symptoms would not require medication or a medical evaluation; signs and symptoms are transient.
- **Moderate:** Discomfort severe enough to cause interference with usual activities; requiring treatment but not extended hospitalization or intensive care for the subject.
- **Severe:** Incapacitating with inability to do work or usual activities; signs and symptoms may be systemic in nature or require medical evaluation and/or treatment; requiring additional hospitalization or intensive care (prolonged hospitalization)

7.4. Relatedness of Adverse Event and Serious Adverse Event

- **Unrelated:** This category applies to those adverse events which, after careful consideration, are clearly and incontrovertibly due to extraneous causes (disease, environment, etc.)
- **Possible:** This category applies to those adverse events for which, after careful medical consideration at the time they are evaluated, a connection with the Investigational Product administration appears unlikely but cannot be ruled out with certainty.
- **Probable:** This category applies to those adverse events which, after careful medical consideration at the time they are evaluated, are felt with a high degree of certainty to be related to the Investigational Product.
- **Definite:** This category applies to those adverse events which, after careful consideration, are clearly and incontrovertibly due to the Investigational Product.

7.5. Expectedness

The PI will be responsible for determining whether an AE or SAE is expected or unexpected. An AE will be considered unexpected if the nature, severity, or frequency of the event is not consistent with the risk information previously described for the study intervention.

7.6. Adverse Event Reporting

AEs will be recorded on the Adverse Event form (Appendix 11.4) by the PI. Changes in the severity of an AE will be documented to allow an assessment of the duration of the event at each level of severity. Changes in severity will necessitate a new CRF to document the new level of severity. AEs characterized as intermittent require documentation of onset and duration of each episode.

Non-serious AEs are to be reported to the study Sponsor on a weekly basis for review, and reported to the IRB per IRB reporting requirements.

7.7. Serious Adverse Event Reporting

The study investigator shall complete an SAE Form (Appendix 11.5) and submit to the study Sponsor and to the reviewing IRB as soon as possible, but in no event later than 48 hours after the investigator first learns of the effect. The study Sponsor is responsible for conducting an evaluation of the SAE and shall report the results of such evaluation to the FDA and to all reviewing IRBs within 10 working days after the Sponsor first receives notice of the effect. Thereafter, the Sponsor shall submit such additional reports concerning the effect as FDA requests.

For questions regarding this process or the event, you may contact your Medline clinical designee or the Medline Associate Director of Clinical Operations:

Name: [name]
[contact]
E-mail: [contact]

8. STATISTICAL CONSIDERATIONS

8.1. Sample Size Determination

As this is an open-label, observational case series, meant to evaluate clinical use of the study product, a formal power analysis was not conducted. Rather, a sample of 20 participants was chosen to provide an initial estimate of product performance in a clinical setting. Data from this study may be used to perform a power analysis for larger, future trial.

8.2. Populations for Analyses

An evaluable dataset will be used to conduct all analyses. Participants who have at least a valid wound assessment at their Initial Visit and their Final Visit, and complied with at least 75% of the dressing changes, will be included in this dataset.

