2.3. Risk/Benefit Profile

2.3.1. Potential Study Risks

Participants may experience irritation or a reddening due to the dressing. Participants will be under the care of a healthcare professional while using the dressing, and he or she will be able to intervene appropriately if the dressing causes any irritation or reddening.

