9.3.2. Safety Oversight

Given that this is a post-market study on a device used in accordance with its labeling, there is minimal safety risk to participants. The PI is a doctor of podiatric medicine and trained in treating these types of wounds. In the event there are any AEs or SAEs, the PI will review them and make any necessary safety determinations as needed.

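### Section 8.2 puts all analyses on one evaluable set, so any adverse event summary would omit most participants who left or stopped the powder early because of an adverse event

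*Combined protocol and SAP*

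**What the plan says.** Section 8.2 defines one population: "An evaluable dataset will be used to conduct all analyses". Two conditions apply. The first admits "Participants who have at least a valid wound assessment at their Initial Visit and their Final Visit". The second requires that they "complied with at least 75% of the dressing changes".

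Section 6.6 fixes what a Final Visit is: "The Final Visit will take place 12 weeks after participant enrollment", or, if healing comes sooner, "the visit where the PI notes complete wound healing will serve as the Final Visit". Section 4.2 ends participation on the same two conditions. Neither section provides a visit for someone who withdraws unhealed.

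Sections 8.3.1 to 8.3.3 cover wound size, BWAT score and pain. No visible part of Section 8 names a safety population or describes an AE summary.

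AE data are nevertheless collected. The schedule in 1.2 lists an AE assessment at every visit from screening. Section 2.3.1 names the risk it foresees: "Participants may experience irritation or a reddening due to the dressing". The AE form in 11.4 codes severity, relationship, seriousness and action taken with the product, including discontinuation.

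**The concern.** A set that requires completion and compliance is a common choice for a supportive efficacy analysis. For tolerability it is a poor one, because stopping is itself a tolerability outcome. A participant who leaves because the dressing irritates the wound is the person a tolerability summary most needs to count, and the rule tends to remove that person.

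The rule is also asymmetric. Leaving early because the wound healed creates a Final Visit. Leaving early because of an AE does not. Whether a participant is analysed therefore depends on how the participant fared.

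The study report is at stake. Section 8.1 presents the study as a first estimate of how the product performs in practice, and says its data may help to size a larger trial. A tolerability figure that leaves out the early stoppers would carry forward into that planning. Section 7.5 also lets the frequency of an event bear on whether it is unexpected, and a frequency needs a denominator of exposed participants, which Section 8 does not supply.

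**Working it through.** The plan gives no figure to reproduce on this point. The check has two parts: who the rule excludes, and what that could do to a reported proportion.

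**1. The Final Visit condition.** Sections 6.6 and 4.2 allow week 12 or complete healing only. A participant who leaves the study before week 12 with an unhealed wound has no Final Visit, so fails 8.2 whatever the compliance up to then.

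**2. The 75% condition**, for someone who stops the powder but still attends at week 12. The inputs are twice-weekly changes (6.4), 12 weeks, and 75% (8.2).

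- Changes due: 2 × 12 = 24. Required: 0.75 × 24 = 18. Reached at 18 / 2 = week 9.
- Schedule in 1.2, every 3 days: 84 / 3 = 28 due, 0.75 × 28 = 21 required, reached at 21 × 3 = day 63, week 9.
- At the window limits: every 4 days gives 21 due and 16 required; every 2 days gives 42 due and 32 required. Both are reached at day 64, about week 9.1.

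Measured against the full schedule, a participant who stops dressing changes before about week 9 fails even if seen at week 12. Section 8.2 does not define the denominator, and 6.4 lets the investigator alter the frequency. If only changes due before stopping count, or a reduced schedule applies, that participant could stay in.

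**3. Size, for discontinuation due to AE.** The documents give no rate, so the count k is an assumption, shown over a range. The calculation takes the case in which every such participant is excluded. Intervals are exact (Clopper-Pearson) 95%. For a zero count out of n, the upper limit is 1 − 0.025^(1/n).

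| k | All 20 treated | Evaluable set |
|---|---|---|
| 1 | 1/20 = 5% (0.1 to 24.9%) | 0/19 = 0% (upper limit 17.6%) |
| 2 | 2/20 = 10% (1.2 to 31.7%) | 0/18 = 0% (upper limit 18.5%) |
| 3 | 3/20 = 15% (3.2 to 37.9%) | 0/17 = 0% (upper limit 19.5%) |
| 4 | 4/20 = 20% (5.7 to 43.7%) | 0/16 = 0% (upper limit 20.6%) |

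The evaluable column barely moves as k grows: the estimate stays at zero and the upper limit stays near 20%.

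**4. How likely it is to matter.** The chance that at least one of 20 participants stops for an AE is 1 − (1 − p)^20. For assumed p of 2%, 5%, 10% and 20% it is 33%, 64%, 88% and 99%.

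**The case against.** The strongest reply is that the plan contains no AE analysis to bias. The endpoints are wound size, BWAT and pain, Section 8.3 analyses those three, and the phrase in 8.2 may have been written with only those in mind. This stands in part: no AE table is planned in the visible text, so the effect on safety follows from the literal wording and is not a stated intention. But the rule has no exception, and an AE summary added to the report under the plan as written would have no other population to use.

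Second, safety handling does not run through 8.2. Non-serious AEs go to the sponsor weekly (7.6), SAEs go to the sponsor and the IRB within 48 hours (7.7), the investigator reviews all of them (9.3.2), and AE review can lead to suspension of the study (9.3.5). This stands in full. A reader might infer that AEs are lost or that surveillance is weakened; the documents do not support that. These routes cover individual cases, however, and give no proportion for the report. The statement in 9.3.2 that "there is minimal safety risk to participants" is a rationale for light oversight, not a summary of what was observed.

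Third, stopping the powder is not the same as leaving the study. As step 2 shows, someone who stops after about week 9 and attends at week 12 stays in, and an earlier stopper might. A reader might infer that every AE stopper is removed; the text supports most, not all.

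Fourth, a reader might take the table as a bias toward zero in the whole AE rate. It is not. It concerns discontinuation due to AE. AEs that do not end treatment would still be counted in evaluable participants.

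**Conclusion.** The point holds in limited form. Section 8.2, read with 6.6 and 4.2, is a stated rule under which an AE summary would leave out most participants who left or stopped early because of an AE. It is more than missing detail, because the only population named is the wrong one for that purpose. The distortion is confined to AEs that lead to stopping, and to summaries in the report.

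In the extreme case that every such participant is excluded, 1 in 20 would be shown as 0/19 and 3 in 20 as 0/17. These counts are assumptions, and fewer exclusions would give a smaller gap. The conclusion also rests on the text available. The part between 8.3.3 and 9.2 could not be checked, and nothing elsewhere names a safety population.

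This should be corrected before analysis. It does not undermine the conduct of the study.

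**What to change.** In Section 8.2, limit the evaluable set to the wound size, BWAT and pain analyses, and add: *Safety set: all participants who received at least one application of the powder.*

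In Section 8.3, add a safety summary on that set:

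- counts and percents of participants with AEs, by severity, relatedness and seriousness;
- the count and percent with discontinuation due to AE, taken from the action-taken code on the form in 11.4.

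Exact confidence intervals are optional in a series of this size. The safety set does not depend on how the 75% denominator is read, so that question need not be settled first.

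The cost is two sentences and one table. The data are already collected, and neither visits nor treatment change.

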1.2. Schedule of Activities (SOA)

REQUIRED ASSESSMENTS	PRE-SCREENING Day -1	SCREENING VISIT Day 0 (May be combined with Initial Visit, Day 1)	INITIAL VISIT Day 1	DRESSING CHANGE VISITS Twice weekly (Every 3 days ± 1 day)	WOUND ASSESSMENT VISITS Once per week Every 7 days ± 2 days (May be combined with Dressing Change Visit)	FINAL VISIT 12 weeks from Initial Visit ³
Pre-Screening Questionnaire ¹	X					
Informed Consent		X				
Screening Form to assess eligibility		X				
Decision on eligibility		X				
Demographics			X			
Wound History			X			
Wound Photograph			X		X	X
Bates-Jensen Wound Assessment			X		X	X
Application of Puracol® Ultra			X	X	X ²	
Pain Assessment for dressing change			X		X	X
Secondary Dressing Notation			X	X	X ²	
Adverse Event Assessment		X	X	X	X	X

1: For participants contacting the research facility, 2: If combined with Dressing change visit, 3: Final visit may occur earlier in the event the participant's wound has completely healed before 12 weeks

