4.2. End of Study Definition

The conclusion of the study for an individual participant will occur at their last Wound Assessment Visit, which will be after twelve weeks of participation or when the wound is completely healed, whichever comes first. The study will be deemed complete upon issuance of the final Clinical Study Report.

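### The only analysis set requires a Final Visit, so participants who leave unhealed before week 12 are dropped from every analysis despite their weekly data

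*Combined protocol and SAP*

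**What the plan says.** Section 8.2 sets up a single population: "An evaluable dataset will be used to conduct all analyses". To enter it, a participant needs a "valid wound assessment at their Initial Visit and their Final Visit, and complied with at least 75% of the dressing changes".

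Three places define when a Final Visit can occur, and they agree:

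- Section 4.2 ends participation at the last wound assessment, "which will be after twelve weeks of participation or when the wound is completely healed, whichever comes first".
- Section 6.6 places the visit at 12 weeks; if the wound closes sooner, "the visit where the PI notes complete wound healing will serve as the Final Visit".
- Note 3 of the Schedule of Activities (section 1.2) says: "Final visit may occur earlier in the event the participant's wound has completely healed before 12 weeks".

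Healing is the only reason given for an early Final Visit. Between the Initial and Final Visits there is a weekly wound assessment, and section 6.5 says "The assessments conducted at this visit will be identical to those described in Sections 6.3.2 to 6.3.4". Those sections cover wound size, pain and BWAT. Sections 8.3.1 to 8.3.3 compare the Initial Visit with the Final Visit. Modelling of the visit-by-visit data is optional and falls under the same analysis set.

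**The concern.** Two participants can both stop attending before week 12 and be treated in opposite ways. One whose wound closes at week 5 has a Final Visit and meets this condition. One who leaves at week 11 with an open wound has no Final Visit and is removed from every analysis, along with the weekly measurements already taken. The condition therefore depends partly on outcome.

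The adverse event and serious adverse event forms list discontinuation as an action taken with the product, so early stopping is foreseen. The available text gives no early-termination visit, no all-treated set and no rule for missing final assessments.

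Section 8.1 gives the purpose as an initial estimate of performance in clinical use, which may feed the power analysis of a larger trial. An estimate restricted to healers and 12-week completers is narrower than that. There is no control arm in which the same selection might partly cancel.

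**Working it through.** **What the plan gives.** N = 20, chosen without a power calculation (8.1). No dropout rate, SD or expected change is stated, so there is no planned figure to reproduce.

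**Who meets the Final Visit condition**

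| Course | Final Visit under 4.2, 6.6 and SOA note 3 | Meets the condition |
|---|---|---|
| Heals before week 12 | Yes, at the healing visit | Yes |
| Unhealed, seen at week 12 | Yes | Yes |
| Leaves unhealed before week 12 | None defined | No |

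**Shift in the mean.** Let k of 20 be excluded, with mean change L, and let the 20 − k kept have mean change M.

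- Mean of all 20 = [(20 − k)M + kL]/20
- Kept mean minus mean of all 20 = (k/20)(M − L)
- For k = 1 this is 0.05 × the gap.

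**Precision.** The 95% CI half-width in SD units is t(0.975, n − 1)/√n, assuming the SD does not change with the set:

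- n = 20: 2.093/4.472 = 0.468
- n = 15: 2.145/3.873 = 0.554

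**Illustration.** The inputs here are assumptions, not document figures: kept mean M = −60% and various leaver means L. The evaluable set reports −60% in every row.

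| k excluded | k/20 | Half-width (SD) | All 20, L = −80% | L = −30% | L = 0% | L = +20% |
|---|---|---|---|---|---|---|
| 2 | 0.10 | 0.497 | −62.0% | −57.0% | −54.0% | −52.0% |
| 3 | 0.15 | 0.514 | −63.0% | −55.5% | −51.0% | −48.0% |
| 5 | 0.25 | 0.554 | −65.0% | −52.5% | −45.0% | −40.0% |

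For k = 5 and L = 0%: (15 × −60 + 5 × 0)/20 = −45%. In the L = −80% column the leavers did better than those kept, and the bias runs against the product.

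**Checking a candidate remedy.** A repeated-measures model with a straight-line time trend would use the weekly data, but it fits healed wounds badly once zeros are carried forward. Take an assumed 10 cm² wound measured at weeks 0 to 12 (13 points, mean time 6, sum of squared deviations of time 182):

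- Closing evenly by week 4: cross-product −125, slope −125/182 = −0.687 per week. Fitted 12-week change = 12 × −0.687 = −8.2 cm² (true −10). Fitted week-12 area = 25/13 − 6 × 0.687 = −2.2 cm².
- Closing evenly by week 8: cross-product −165, slope −0.907 per week. Fitted change −10.9 cm², more than the whole wound. Fitted week-12 area = 45/13 − 6 × 0.907 = −2.0 cm².

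A straight-line model should therefore not carry the main result.

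**The case against.** The strongest defence is one of scale. This is a 20-person descriptive case series with no power analysis. Its t-tests are labelled exploratory and it has no success threshold. The evaluable rule is prespecified and visible to any reader, and no dropout figure shows that anyone will be lost. That defence stands as a limit on severity: no error rate or pass/fail decision is affected. It does not answer the point that observed data are discarded by a rule tied to outcome, when the estimate is the study's product.

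A reader might infer more than the documents support in four ways:

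- **That only healers are analysed.** Unhealed participants seen at week 12 meet the Final Visit condition.
- **That the result must be too favourable.** This needs unhealed leavers to have done worse than those kept, which is plausible but stated nowhere.
- **That the 75% rule rests on two conflicting totals.** The SOA reads "Twice weekly (Every 3 days ± 1 day"), from which one could compute 2 × 12 = 24 or 84/3 = 28 changes, with cuts of 18 or 21. No section states 28 or any total. Twice weekly also appears in the synopsis, section 6.4 and the pre-screening form, and alternating 3- and 4-day gaps satisfy both descriptions.
- **That fully adherent early healers fail the 75% rule.** At twice weekly, a participant healing at week 6 scores 12/24 = 50% only if a fixed 12-week count is imposed. Participation ends at healing, and section 6.4 says "Ultimate determination of dressing change frequency will reside with the PI", so the natural reading is changes due for that participant: 12/12 = 100%. Missed visits should also be traceable through deviation reporting (9.4).

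The text between sections 8.3.3 and 9.2 was not available. A further missing-data rule there cannot be excluded, though the wording of 8.2 makes a second analysis set unlikely.

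**Conclusion.** The Final Visit condition should be changed. As written, 8.2 together with 4.2, 6.6 and SOA note 3 keeps early healers and removes unhealed leavers, whatever weekly data they have. This follows from the definitions and needs no outside assumption.

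The size and direction of the bias cannot be derived. What can be said is that each exclusion carries a weight of 5% of the gap, and that the interval widens by 0.554/0.468 − 1 = 18% if 5 are lost (assumed number, constant SD). The harm falls on the reported mean change, its 95% CI and any power calculation built on them. The 75% rule lacks a stated count, which is missing detail rather than a demonstrated flaw.

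**What to change.** **Main analysis.** Define the main set as all participants with a baseline assessment and at least one application of the powder. Report change from baseline to the last available assessment, taking 0 cm² if healed, with its 95% CI and the median. State that a participant with no later assessment contributes no change. For BWAT and pain, use the last observed scores; a healed BWAT has a floor of 9 (items 1 to 4 at 0, nine items at 1), not 0.

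**Supportive analysis.** Keep the evaluable set alongside, and tabulate exclusions with reasons.

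**Sensitivity analyses**

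- A repeated-measures model of the weekly data whose time trend is not forced to be a straight line, with the missing-at-random assumption stated. If zeros are carried forward after healing, state the no-recurrence assumption.
- Because a last available value may understate worsening after exit, a less favourable assumption for unhealed leavers, such as no change from baseline (keeping the last value where it is already worse than baseline).

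**Minor clarification.** Count the 75% against the changes scheduled or PI-directed for that participant up to healing or exit, and reconcile the SOA, 6.4 and 8.2 on that count. The Dressing Log as printed has no field for the number due, so it should be noted somewhere.

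**Cost.** Revised analysis wording, some extra programming and that one added record; no new visits. The headline estimate may be less favourable.

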1. PROTOCOL SUMMARY

1.1. Synopsis

Title: A prospective case series evaluating a fibrillar collagen powder dressing to treat chronic, stalled lower-extremity wounds

Study Description: Chronic wounds are a source of significant morbidity and escalating healthcare costs. The wound care professional has a myriad of modern wound dressings to choose from when treating a wound, each of which has benefits and drawbacks. An understanding of how a given dressing performs in healing a particular wound is crucial in order to determine a clinical mapping of wound dressings to wound types; such a categorization would lead to more efficient clinical decision making and better patient outcomes. This case series will evaluate the ability of a fibrillar collagen powder to improve healing of chronic, stalled, lower-extremity wounds.

Objectives: Evaluate the ability of a fibrillar collagen powder dressing to treat chronic, stalled, lower-extremity wounds

Endpoints: **Primary:** Change in wound size over twelve week period
Secondary: 1) Change in Bates-Jensen Wound Assessment Tool score, 2) Change in reported pain level.

Study Population: Twenty adult patients with chronic lower-extremity wounds (i.e. below the knee) of greater than four weeks that have failed to respond to at least one advanced wound dressing treatment. Specific wound types include: pressure ulcers, diabetic ulcers, and venous leg ulcers.

Phase: Post-Market

Description of Sites/Facilities Outpatient podiatry clinics in the United States
Enrolling Participants:

Description of Study Intervention: Patients who meet the inclusion criteria will be provided with fibrillar collagen powder dressing (Puracol® Ultra Powder by Medline Industries, Inc.). The powder dressing will be used in

accordance with its label. After cleansing the wound by the clinical site staff, the powder is placed directly on the wound, and then the wound will be covered with an appropriate moisture retentive secondary dressing. Patients will visit the clinic twice a week to have the powder re-applied. Wound evaluations will take place once a week at the outpatient clinic, with the intervention lasting up to twelve weeks. Concurrent standard of care, such as compression for venous ulcers, will be provided.

Study Duration: Total time for study completion to allow accrual of all subjects, and appropriate treatment as per the protocol, will be approximately 12-18 months

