8.3. Data Analysis

8.3.1. Wound Size Analysis

Descriptive statistics for initial wound size (measured at the Initial Visit) and final wound size (measured at Final Visit) will be calculated. These statistics include measures of central tendency (e.g. mean, median), variability (e.g. standard deviation). A 95% confidence interval for mean wound size change will also be calculated, assuming normality of the data. For exploratory purposes, a paired samples t-test will be conducted on wound size at the Initial Visit vs. Final Visit to identify any significant differences in wound size over the course of the study; if the data are not normally distributed, a non-parametric test will be used. Finally, change in wound size over time, using data from each visit may be modeled, using other variables such as demographic and baseline data, to better understand predictors of wound closure.

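### Section 8.2 drops participants with both wound measurements from the only analysis set if dressing-change compliance is under 75%, which can bias the estimated change in either direction

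*Combined protocol and SAP*

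**What the plan says.** Section 8.2 sets up a single analysis population: "An evaluable dataset will be used to conduct all analyses". Two conditions must both be met. The first concerns measurement: "Participants who have at least a valid wound assessment at their Initial Visit and their Final Visit". The second concerns adherence: the participant must also have "complied with at least 75% of the dressing changes, will be included in this dataset". Neither *complied* nor the denominator of the 75% is defined.

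The primary endpoint (Section 1.1) is "Change in wound size over twelve week period". Section 8.3.1 estimates it from the Initial and Final Visit sizes: "A 95% confidence interval for mean wound size change will also be calculated, assuming normality of the data". Sections 8.3.2 and 8.3.3 use the same two visits for BWAT and pain. Sections 8.1 to 8.3 plan no all-treated set, no sensitivity analysis and no listing of excluded participants.

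On purpose, Section 8.1 states that "a sample of 20 participants was chosen to provide an initial estimate of product performance in a clinical setting", and adds that the data may be used to power a later trial. On dressing frequency, Section 6.4 states: "Ultimate determination of dressing change frequency will reside with the PI, in the event the twice weekly visits conflicts with the patient's clinical needs". The Adverse Event Form (Section 11.4) has codes for the product being modified, interrupted or discontinued.

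**The concern.** The participants at issue have no missing primary data. They are set aside because of something that happens after treatment starts. A participant whose product is interrupted or discontinued for an adverse event can still attend at week 12, be measured, and then be removed for low compliance. A schedule altered by the PI under Section 6.4 might have the same effect, depending on how *complied* is read. The excluded participants may therefore differ systematically in outcome from those kept.

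There is no control arm, so the Initial-to-Final change is the whole result and nothing offsets this selection. The set describes participants who kept to the schedule, whereas Section 8.1 asks about performance in a clinical setting. Any bias would also pass into a power calculation for a later trial.

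**Working it through.** **Inputs.** Planned n = 20 (Section 8.1). Dressing changes are twice weekly for up to 12 weeks (Sections 1.1 and 6.4), so 2 × 12 = 24. The Section 1.2 interval of every 3 days would give 84/3 = 28. The compliance threshold is 75% (Section 8.2). There is no derived figure to reproduce, because "a formal power analysis was not conducted". The documents give no effect size, SD, dropout rate or compliance rate, so the numbers in steps 2 to 4 are illustrations that assume all 20 participants have both assessments.

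**1. Who is removed.** With 24 changes due, 0.75 × 24 = 18, so a participant who misses 7 or more is excluded. With 28 due, 0.75 × 28 = 21, so 8 or more. Each excluded participant is 1/20 = 5% of the planned sample.

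**2. Bias.** Let *k* of 20 measured participants be excluded, with mean change equal to *r* times the mean change of those kept. The all-measured mean is ((20 − *k*) + *rk*)/20 of the reported mean, so

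relative error = 20/((20 − *k*) + *rk*) − 1.

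| *k* | *r* = 0 (no improvement) | *r* = 0.5 | *r* = 1 (same as kept) | *r* = 2 (twice the improvement) |
|---|---|---|---|---|
| 2 | +11.1% | +5.3% | 0 | −9.1% |
| 3 | +17.6% | +8.1% | 0 | −13.0% |
| 4 | +25.0% | +11.1% | 0 | −16.7% |
| 5 | +33.3% | +14.3% | 0 | −20.0% |

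For *k* = 4: 20/16 − 1 = 25.0%, 20/18 − 1 = 11.1%, and 20/24 − 1 = −16.7%. The *r* = 2 column corresponds, for example, to a 50% mean reduction in those kept and complete healing in those excluded. A positive sign means the reported reduction is too large.

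**3. Why the sign depends on the denominator.** Participation ends at complete healing (Sections 1.1 and 4.2). Suppose the 75% is counted against a fixed 24 changes. A fully adherent participant who heals at week 8 has 16/24 = 67% and is excluded; one who heals at week 9 has 18/24 = 75% and stays. That reading removes the fastest healers. If the denominator is the changes due up to the participant's own Final Visit, the week-8 healer has 16/16 = 100% and stays. The second reading fits the end-of-participation rule better, but Section 8.2 does not state it.

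**4. Precision.** The 95% CI half-width in SD units is t(0.975, n − 1)/√n:

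| n analysed | Half-width |
|---|---|
| 20 | 0.468 SD |
| 18 | 0.497 SD |
| 16 | 0.533 SD |
| 15 | 0.554 SD |

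At a given SD, excluding measured participants widens the interval.

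**The case against.** The strongest reply is that this is a small descriptive case series with exploratory tests, that the threshold is prespecified and openly stated, and that an adherence-defined set answers a legitimate question about a product. All of that is true. It supports keeping the 75% subset as an analysis, but not making it the only one when the stated aim is performance in a clinical setting.

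The affected group may also be very small. Pre-screening asks whether the person can attend twice weekly (Section 11.2.1), those judged unable to follow the protocol are excluded (Section 5.2), and reminders are sent (Section 5.3). Some participants whose treatment is interrupted may also lack a Final Visit, and would be absent with or without the 75% rule. This limits the likely size of the problem, which the documents do not allow anyone to estimate.

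Three stronger readings are tempting, and the documents do not support them:

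- *The rule overstates performance.* Sections 6.4 and 11.4 show that dressing changes can be altered or interrupted. They do not show that the wounds concerned did worse. Participants doing well might also miss visits, and a fixed denominator would remove early healers.
- *The rule makes the confidence interval too narrow.* Fewer participants widen it at a given SD. It would narrow only if the exclusions reduced the SD enough, and nothing in the documents indicates that.
- *A PI-altered schedule leads to exclusion.* A participant who follows the altered schedule can naturally be regarded as having complied, and the product label leaves change frequency to need (Section 11.1.1). Section 8.2 leaves this open.

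**Conclusion.** The point holds in this form: Section 8.2 discards observed primary outcomes on a post-baseline criterion that can be related to outcome, and no other analysis set compensates. The estimate can be biased, and it describes a different group from the one Section 8.1 refers to.

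Neither direction nor size is established. With 4 of 20 excluded, the assumed scenarios run from a 25.0% overstatement (no improvement in those excluded) through zero (same mean change) to a 16.7% understatement (twice the improvement). These rest on assumed *k* and *r*. The planned estimate is a mean change in cm² for wounds of 1 to 100 cm² at entry, so the effect of any one exclusion also depends heavily on that wound's starting size. The loss of precision, from 0.468 to 0.533 SD at n = 16, assumes an unchanged SD.

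The consequence is a potentially biased descriptive estimate and planning input, not a failed confirmatory test. The change is worth making because it is cheap.

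**What to change.** In Section 8.2:

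1. Delete the 75% condition from the main analysis set, so that every treated participant with valid Initial and Final assessments is analysed for wound size, BWAT and pain, whatever the number of dressing changes.
2. Keep the 75% compliant subset as a labelled supportive analysis. Define its denominator as the changes due up to the participant's own Final Visit under the schedule in force for that participant.
3. Report how many measured participants the subset leaves out, with their individual wound-size changes.

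This costs a short amendment to 8.2 and one repeat run of the same summaries, with no new visits or data. The downside is that the headline estimate may be less favourable or more variable. The change does not address participants without a valid Final Visit, who remain outside the main set.
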